Fluoroquinolones are contraindicated with patients with known history of myasthenia gravis, because they have neuromuscular blocking activity and may exacerbate muscle weakness.

The overdose may lead to loss of appetite, diarrhea, metallic taste, headache, dizziness, insomnia or drowsiness.

The following is a list of possible side effects that may occur, rarely, from the use of Ciprofloxacin[®] tablets:

- Allergic reactions such as rash, itching, and swelling of the mouth, face, lips, or tongue
- Nausea, headache, anorexia, diarrhea, unpleasant metallic taste, stomach cramps pain, vomiting, fainting, and fever.
- Reversible neutropenia (leukopenia), and blood dyscrasias.
- Dysuria, darkening of urine, cystitis, bloody stools, abdominal and vaginal yeast infection.
- Tendon inflammation and damage.
- Irregular heartbeat and loss of consciousness.
- Mood or mental changes such as anxiety, confusion, depression, and sleeplessness.
- Convulsive seizures and peripheral neuropathy tremors.
- Jaundice.

8.5.1 Storage and Drug Accountability:

Study drugs are to be stored at room temperature up to 30 degrees C (86 degrees F). Keep them in the original containers. Store away from heat, moisture, and light. Do not store in the bathroom. Keep them out of the reach of children and away from pets.

All empty, partially used, and unused blisters will be retained by the Investigator (at room temperature) until they are returned to the pharmacist and to be checked by monitor.

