8.6 Risks & Benefits of study drug

Benefit: Ciprodiazole[®] (Ciprofloxacin & Metronidazole) is active against a broad spectrum of aerobic/anaerobic bacteria. So, it is indicated in pelvi-abdominal infections and/or following IV antibiotics in post-operative period, for pelvi-abdominal surgeries or acute conditions, it will be supplied by the sponsor.

Risk: The most frequently reported side effects of ciprofloxacin are nausea, diarrhea, liver function tests abnormality, vomiting, and rash.

The most common side effects of Metronidazole are allergic reactions such as skin rash, swelling of the face, lips, tongue or throat, fever or difficulty in breathing.

8.7 Discontinuation and Modification of Dosing of Ciprodiazole[®]:

- The usual dose should be reduced in patients with severe renal disease
- In the event that a positive result is obtained on a pregnancy test for a patient, the administration of Ciprofloxacin and Metronidazole must be discontinued immediately.

8.8 Concomitant Medication:

Throughout the study, Investigators may prescribe any concomitant medications or treatments deemed necessary to provide adequate supportive care except for those listed in the exclusion criteria. If these are required, the participant will be withdrawn. A medication, other than the study medication (Ciprofloxacin or Metronidazole) taken during the study will be recorded in the CRF.

Any medication or vaccine (including over-the-counter or prescription medicines, vitamins and/or herbal supplements) that the subject is receiving from 2 weeks prior to study drug administration and during the study, must be recorded in the paper case report form along with the reason for use, date(s) of administration including start and end dates, and dosage information including dose, route and frequency.

The investigator should review all concomitant medications for any potential interactions.

Ciprodiazole[®] Tablets (Ciprofloxacin hydrochloride & Metronidazole) is contraindicated with administration of tizanidine, because this may cause low blood pressure and sleepiness

Ciprodiazole[®] Tablets is contraindicated with administration of antacids containing magnesium and aluminum, supplements and other products containing calcium, iron or zinc because they reduce the effect of Ciprofloxacin.

Metronidazole potentiates the anticoagulant effect of Warfarin and other oral coumarin anticoagulants resulting in a prolongation of prothrombin time.

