4. Subjects who are willing to sign Informed Consent Form (ICF) and ready to comply with the protocol for the duration of the study

10.2.2 Exclusion Criteria:

Subjects presenting with any of the following will not be included in the study:

1. Subjects with a history of hypersensitivity to any of the active ingredients of the treatments used
2. Subjects who are receiving or received any other antibiotics during the previous two weeks, rather than IV treatment in the first post-operative 48 hours, mentioned in the protocol (Metronidazole injection plus third generation cephalosporin)
3. Subjects with Pelvi-abdominal infection and performed surgery after failure of oral antibiotics.
4. Subjects having surgeries such as colorectal surgeries, appendectomy and ovarian cystectomy
5. Subjects with any medical condition requiring the usage of the following medications:

- a. Drugs that induce microsomal liver enzymes, such as Phenytoin or Phenobarbital, may accelerate the elimination of metronidazole
 - b. Drugs that decrease microsomal liver enzymes activity, such as cefrimide, may prolong the half-life and decrease plasma clearance of metronidazole.
 - c. Administration of theophylline in combination with Ciprofloxacin may lead to cardiac arrest, seizures, status epilepticus, and respiratory failure
 - d. Administration of corticosteroids in combination with Ciprofloxacin may lead to tendinitis
 - e. Antacids containing magnesium and aluminum, supplements and other products containing calcium, iron or zinc as they reduce the effect of Ciprofloxacin.
 - f. Tizanidine because this may cause low blood pressure and sleepiness
6. Subjects with uncontrolled diabetes mellitus; FBG > 200 mg/ml
 7. Subjects with renal impairment (S. Creatinine > 1.5 mg/dL)
 8. Subjects with hepatic impairment (Child-Pugh Score B-C)
 9. Subjects with liver enzymes (SGOT, SGPT) > 2 times Normal range.
 10. Pregnant or breast feeding women

10.2.3 Discontinuation/Withdrawal of participants from the study:

Each participant has the right to withdraw from the study at any time.

In addition, the investigator may discontinue a participant from the study at any time if the investigator considers it necessary for any reason including:

1. Ineligibility (either arising during the study or retrospective having been overlooked at screening)
2. Significant protocol deviation
3. Significant non-compliance with treatment regimen or study requirements

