4. Disease progressions which requires discontinuation of the study medication or results in inability to continue to comply with study procedures.
5. Consent withdrawn by subject.
6. Lost to follow up
7. SAE or death
8. If a female subject becomes pregnant
9. Subjects which have Cholecystitis and it will be operated upon.

The reason for withdrawal will be recorded in the CRF. If the participant is withdrawn due to an adverse event, the investigator will arrange for follow-up visits or telephone calls until the adverse event has resolved or stabilized.

10.2.4 Assessments to be done:

1- Screening Visit Assessments:

- The enrollment period will be 12 months including the screening visit. Screening assessments will be completed and treatment will be initiated within visit 1.
- During this visit, patients will be screened for fulfillment of the inclusion and exclusion criteria and written informed consent will be obtained.
- Screening assessments will include physical examination, medical history, patient demographics, vital signs, concomitant medications, safety laboratory tests

(including Fasting Blood Sugar (FBS), Total leukocyte count, Liver enzymes (SGOT & SGPT), Total Bilirubin and S. Creatinine), Child-Pugh Score (for hepatic impairment) and, β -HCG (for females of child bearing potential only) and pelvi-abdominal Ultrasound & others.

- Presence of any signs/symptoms of post-operative wound infection such as redness, fever or wound discharge will be recorded (in case of post-operative subjects)

2- Follow-up 1 Visit:(Day 8):

- On-treatment assessments include physical examination, vital signs, AEs, SAEs, concomitant medication and study drug dosing compliance
- Days for complete healing will be checked
- Complete resolution, improvement, failure or relapse of Pelvi- abdominal infection
- Presence of any signs/symptoms of post-operative wound infection such as redness, fever or wound discharge will be recorded (in case of post-operative subjects)

3- Follow-up 2 Visit & End of study visit (Day 15):

- Assessments include physical examination for vital signs, AEs, SAEs, concomitant medication, and study drug dosing compliance
- Pelvi-abdominal Ultrasound and others will be done, if needed upon Physician's decision.
- Days for complete healing will be checked
- Complete resolution, improvement, failure or relapse of Pelvi- abdominal infection

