12.2 Patient Enrollment

After signing the informed consent form, each potential subject will be screened for eligibility based on the inclusion and exclusion criteria specified. Randomization will be done.

All visits will occur as closely as possible to the scheduled visit dates with window of 3 days. In case of a premature discontinuation of the study, the subject, will be, if possible called in for a last visit. Even if the subject would not be able to attend, the 'End of Study' forms will be completed .

12.3 12.3 Schedule of visits

Table 1: Schedule of Visits

Observation	Visit 1 (Screening & treatment)	(Follow-up 1 V)	(Follow-up 2 V) End of Study
Time lines	Day 0	Day 8	Day 15
Informed consent document signed	X		
Review Inclusion/Exclusion criteria	X		
Patient Demographics	X		
Significant medical history and current disease status	X		
Physical examination	X	X	X
Vital Signs	X	X	X
Child-Pugh Score	X		
Concomitant medications	X	X	X
Safety Laboratory Tests:			
FBS	X		
Total Leucocytic count	X		X
SGOT (ALT)	X		X
SGPT (AST)	X		X
Total Bilirubin	X		X
S. Creatinine	X		X
Serum β -HCG: (for females in childbearing period)	X		
Pelvi-abdominal Ultrasound & others (Optional)	X		X
Study Drug Dispensed	X	X	
Drug Accountability		X	X

Observation	Visit 1 (Screening & treatment)	(Follow-up 1 V)	(Follow-up 2 V) End of Study
Time lines	Day 0	Day 8	Day 15
Presence of any signs/symptoms of post-operative wound infection such as redness, fever or wound discharge. (in case of post-operative subjects)	X	X	X
Days for complete healing		X	X
Complete resolution, improvement, failure or relapse of pelvi - abdominal infection		X	X
AE		X	X
SAE		X	X
Study Completion Form			X

The subsequent visits will occur as follows :

- **Visit 1 (Screening & treatment initiation Visit):** Day 0
- **Follow-up V1:** Day 8 (+/-) 3 days
- **Follow-up V2 & End of Study Visit:** Day 15 (+/-) 3 days

12.3.1 Visit 1 (Screening & treatment initiation):

- During this visit, subjects will be informed about the study. If they are willing to participate in the study, they will sign the written ICF. A copy of the signed ICF will be given to the subject. In addition, the subjects will be evaluated for study eligibility according to the inclusion and exclusion criteria.
- Screening Assessments will include: physical examination, vital signs, demographic data (Age & Gender), medical history and concomitant medications.

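### Protocol 8.8 and 10.2.3 do not separate stopping study drug from leaving the study, so later adverse events and end-of-study labs can be lost for withdrawn patients

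*Protocol*

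**What the plan says.** Protocol 8.8 lets investigators prescribe supportive treatment except for the medicines in the exclusion criteria. Of those it says: "If these are required, the participant will be withdrawn". Exclusion criterion 5 (10.2.2) includes corticosteroids, certain antacids, and products containing calcium, iron or zinc.

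The section that governs withdrawal, 10.2.3, is headed "Discontinuation/Withdrawal of participants from the study". It is permissive: "the investigator may discontinue a participant from the study at any time". Its reasons include an SAE or death (item 7). Item 4 places a need to stop drug among the reasons for leaving the study: "Disease progressions which requires discontinuation of the study medication or results in inability to continue to comply with study procedures".

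Some follow-up survives withdrawal:

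- 10.2.3: "If the participant is withdrawn due to an adverse event, the investigator will arrange for follow-up visits or telephone calls", until the event has resolved or stabilized.
- 12.2: a patient who stops prematurely is "if possible called in for a last visit". Sections 12.3.1 and 12.3.2 repeat this.
- 13.2: all adverse events are followed to resolution or stabilization. It adds that only unresolved events are followed actively and that new ones are not actively looked for in that period.

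The primary safety analysis (Protocol 10.7.6, SAP 8.6) covers the first visit to the end-of-study visit. Laboratory tests are scheduled only at Visit 1 and Day 15 (Table 1 of the Protocol).

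**The concern.** The plan has one word, withdrawn, for two different states: no longer taking study drug, and no longer being observed. A safety comparison over a fixed window needs the second to happen as rarely as possible. If needing a barred medicine takes a patient out of the study, the planned questioning about adverse events at the remaining visits goes with it. So may the end-of-study leukocyte count and liver enzymes, which are secondary safety endpoints (10.3.2).

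The study is open label, so whoever decides on withdrawal knows the arm. Neither 10.7.6 nor SAP 8.6 says how incompletely observed patients are counted. The SAP shells for Tables 4 to 8 fix the denominator at 156 per group, so an early leaver kept in that denominator is treated as free of anything that happened later.

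**Working it through.** **Reading the text.** The documents give no rate of withdrawal or of adverse events, so there is no figure of the plan's own to reproduce. The check is mainly of wording.

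1. *Is withdrawal required?* For a barred medicine, yes (8.8). For an SAE, no; 10.2.3 only permits it.
2. *From what?* Section 8.8 does not say. The only section defining withdrawal (10.2.3) concerns the study. Where section 8.7 means stopping drug, after a positive pregnancy test, it says that administration is discontinued. The natural reading of 8.8 is therefore leaving the study, but the text is ambiguous.
3. *What data collection remains?* Section 10.2 describes consent to collection while the subject is on the study. After withdrawal there remain follow-up of known events and one last visit if it can be arranged. No section keeps Day 8 and Day 15.
4. *Are new events sought?* Not actively (13.2), although 13.2 also says patients are asked about adverse events at each contact. The gap is widest for a patient withdrawn with no unresolved event, who has only the possible last visit.
5. *Are labs secured?* Section 12.3.2 calls for end-of-study labs when infection has completely resolved at Day 8. Its premature-discontinuation item mentions none.
6. *What is lost?* The event that prompted withdrawal is recorded and counts under the one-dose safety population of 10.7.1 and SAP 8.1. (The definition of ITT in 14.2 requires a post-baseline visit; that inconsistency is a separate matter.) What can be lost is any later, different AE or SAE, and the end-of-study laboratory values.

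**Illustration of size; every rate is assumed.** A patient who leaves at Day 3 loses (15 − 3)/15 = 80% of the planned window; at Day 8, (15 − 8)/15 = 47%.

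Let p be the 15-day risk of a later new event (constant hazard), w the share of an arm leaving at day t, with nothing new collected afterwards.

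- Observed proportion = (1 − w)p + w[1 − (1 − p)^(t/15)].
- Example: p = 10%, w = 5%, t = 3. Then 1 − 0.90^0.2 = 0.0209, and observed = 0.95 × 0.10 + 0.05 × 0.0209 = 0.0960. Missed: 0.0040/0.10 = 4.0%, or 0.62 patients per 156.
- Over p = 2% to 20%, w = 2% to 10% and t = 3 or 8: 0.9% to 8.0% of later events missed, or 0.03 to 2.4 patients per 156.

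If leavers carry a higher risk q = RR × p, the true proportion is (1 − w)p + wq, and q replaces p in the bracket above. With t = 3, RR = 3 or 5, p = 5% or 10% and w = 5% or 10%:

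- Share missed: 10.5% (p = 10%, w = 5%, RR = 3) to 27.7% (p = 5%, w = 10%, RR = 5).
- Patients per 156: from (0.0550 − 0.0491) × 156 = 0.9 to (0.1400 − 0.1029) × 156 = 5.8.

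**The case against.** The strongest reply is that the plan already protects safety follow-up. A patient withdrawn because of an adverse event gets visits or calls; all adverse events are followed to resolution or stabilization; patients are asked about events at every contact and have a number to call at any hour (13.2); and a last visit is attempted. This is right as far as it goes. A reader might infer that withdrawal ends safety follow-up, and the documents do not support that. What ends is the planned search for new events.

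A reader might also say that the primary safety endpoint is censored. It is an incidence (10.3.1) compared as counts by chi-square, not a time to event, and a patient withdrawn with a side effect already counts as having one.

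Third, it is tempting to argue that treating a named side effect triggers withdrawal: 8.5 lists "Allergic reactions such as rash, itching, and swelling of the mouth, face, lips, or tongue", and corticosteroids are barred. No section says that the one would be used for the other, and 8.5 calls these effects rare. That link is clinical inference. Where it did occur, the withdrawal could fairly be called AE-related, so the 10.2.3 follow-up would apply.

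Fourth, the two states are not wholly merged. Events leading to permanent drug discontinuation, and causes of discontinuation, are tabulated (10.7.6, SAP Tables 6 and 7), and 12.3.2 allows treatment to end at Day 8 with a return at Day 15. Section 8.8 also sits in the treatment chapter, so withdrawn could mean from drug only. This stands as an argument that the text is ambiguous. It does not supply a visit schedule for the withdrawn patient.

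Finally, continued collection may need consent wording (10.2), and some patients with complete resolution finish at Day 8 (12.3.2). Both objections stand, and the fix has to deal with them.

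**Conclusion.** The point holds in a limited form. As written, a patient who needs a barred medicine must be withdrawn, the only withdrawal section means leaving the study, and nothing keeps that patient's remaining visits or end-of-study labs beyond a last visit that may not happen. Later, different AEs or SAEs and the final leukocyte and liver-enzyme values can be lost inside the window that the safety analyses claim to cover.

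The size cannot be derived from the documents. The illustration gives roughly 1% to 8% of later events missed at equal risk, and about 10% to 28% if leavers carry three to five times the risk. All of this rests on assumed withdrawal, timing and event rates, and on nothing new being collected after exit, which 13.2 and the possible last visit partly soften.

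A reader might infer that the comparison is biased toward no difference. That would need unequal withdrawal or unequal later risk between arms, and the documents give no figures for either, so the direction is open too. This is a clarification worth making because it is cheap. It does not by itself show that the safety result is unreliable.

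**What to change.** Leave every clinical reason for stopping treatment as it is. Change only what happens to data collection afterwards.

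1. In 8.8 and 10.2.3, state whether withdrawn means from study drug or from the study.
2. For patients who stop drug without withdrawing consent, being lost to follow-up or dying, keep the scheduled Day 8 and Day 15 assessments: AEs and SAEs, wound and infection status, and the end-of-study labs. If the patient cannot attend, make a telephone contact about adverse events.
3. In 10.7.6 and SAP 8.6, state that adverse events up to one cut-off count whether or not drug was stopped. Apply the same cut-off to all patients, including those who complete at Day 8 under 12.3.2; otherwise patients who stop drug would be observed for longer than those who resolve early.
4. Reconcile 8.8, 10.2, 10.2.3, 12.3.2 and 13.2 with this, including the statement that new events are not actively sought.

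The cost is protocol and SAP wording, a few retained visits, some telephone contacts that the plan does not now include, and a check that the consent text in line with 10.2 covers collection after drug is stopped.

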10.5 Study Size

Subjects having pelvi-abdominal infection, in post-operative period of pelvi-abdominal surgeries or acute conditions will be selected from the surgical department in Menoufia University Hospital and some subjects might be referred from other departments in Menoufia University Hospital such as and not limited to; the department of Gynecology and Obstetrics. Patients will be asked to participate in the study and sign the informed consent, then screening for inclusion and exclusion criteria will be done and recorded in the patient's medical records (either enrolled or screening failure).

10.5.1 Determination of Sample Size

As the primary objective is to assess the safety of oral Ciprodiazole[®] tablets (Ciprofolxacin /Metronidazole) versus currently used Ciprofloxacin Tablets & Metronidazole tablets following IV antibiotics in post-operative period, for pelvi-abdominal surgeries, and based on the previous study "Comparison of Intravenous/Oral Ciprofloxacin Plus Metronidazole Versus Piperacillin / Tazobactam in the Treatment of Complicated Intra-abdominal Infections".^[15] Overall clinical resolution rates were statistically superior for CIP+MET (74%) compared with PIP/TAZO (63%). Mean length of stay was 14 days for CIP1MET and 17 days for PIP/TAZO patients.

So, the following parameters are used to calculate the expected sample of the study:

- Design: non-inferiority
- Sample Size = 312 Subjects (1:1)
- Ciprodiazole Sample Size (Experimental group) = 156 subjects
- Current used regimen Sample Size (Control group) = 156 subjects
- Confidence level 95% (α error = 5%)
- Power = 80%
- Non-Inferiority margin = 2%

10.5.2 Sample Size & Treatment Groups:

Total of 312 Egyptian patients who have pelvi-abdominal infection or started IV antibiotics in post-operative period, for pelvi-abdominal surgeries will be enrolled in the study and randomized, using a computer system, with a ratio of 1:1, into two categories as follows:

1. Group will receive Ciprodiazole[®] tablets; 156 patients
2. Group will receive Ciprofloxacin Tablets & Metronidazole tablets; 156 patients

10.5.3 Randomization:

Subjects will be randomized into the two treatment groups with a balanced ratio of 1:1. Randomization by block Computer-generated randomization lists will be established by Data Management department (DM) of CRO (Nagy Research). The number of patients of the two treatment groups will be balanced (ratio 1:1). (156 Ciprodiazole[®]: 156 Ciprofloxacin Tablets & Metronidazole tablets).

A document describing the procedure of constitution of the randomization lists will be stored confidentially at Nagy Research CRO

Block size: 2, 4

The Randomization list will be done using website:
(<https://www.sealedenvelope.com/simple-randomiser/v1/lists>)

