This study is a clinical trial that will enroll 312 patients, who had pelvi-abdominal infection and/or started IV antibiotics for 48 hours, post-operative or till be able to tolerate oral intake in post-operative period, for pelvi-abdominal surgeries. They will be divided into two

treatment groups; group A: patients are treated with Ciprofloxacin[®] tablets (Ciprofloxacin/Metronidazole) and group B (control group): patients are treated with the currently used Ciprofloxacin Tablets & Metronidazole tablets, using computer-generated randomization list, generated by the Data Management department (DM) of the CRO (Nagy Research) for the 2 groups who will be enrolled in this study will agree to the release of information and sign an informed consent. Subjects included in this study are enrolled for the collection of data that reflect the care they receive under routine clinical circumstances. All provided care should be according to protocol and the local standard of medical care.

The screening and enrollment period is planned to be 12 months. Subject will start receiving the treatment for a duration not exceeding 15 days. And with post-operative cases, subject will start receiving the treatment after IV antibiotics for 48 hours or till be able to tolerate oral intake. Follow up will be for 15 days from enrolment till End of treatment.

10.2 Study Setting:

Subjects will consent to the collection of study related information while on the study. Subjects will be informed that data will be collected about their health while they are enrolled in this study. They may choose to withdraw at any time. Subjects will be advised that data collected in this study will be provided to the Sponsor, and may be reported to regulatory authorities or published in scientific journals. In any of these events, the subjects' identities will not be revealed.

10.2.1 Inclusion Criteria:

Subjects meeting all of the following criteria will be considered for enrollment in the study:

1. Egyptian male and female patients aged between 18-65 years' old
2. Subjects having pelvi-abdominal infections such as and not limited to: Ulcerative colitis, Diverticulitis, Cholecystitis, and PID (e.g oophoritis and salpingo-oophoritis).
3. Subjects during post-operative period for pelvi-abdominal surgery and following IV medication with Metronidazole injection plus third generation cephalosporin.

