10.7 Data Analysis

10.7.1 Analysis populations

Analysis of all efficacy variables will be performed only for patients who completed the study without protocol violation (as per protocol).

Analysis of all safety variables will be performed for all patients (intent-to-treat population), who received even 1 dose of the treatment; either Ciprodiazole[®] tablets or currently used Ciprofloxacin Tablets & Metronidazole tablets.

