10.7.6 Primary Safety analysis

A. Number of participants experiencing Serious Adverse Events (SAEs). [Time Frame: visit 1 to End of study visit].

- Frequency distribution (number & percent) of occurrence of SAEs necessitating a change or discontinuation of treatment. Chi² test will be used to determine *p*-value and significance between the 2 groups.
- Frequency distribution (number & percent) of type and severity of SAEs. Chi² test will be used to determine *p*-value and significance between the 2 groups.

B. Number of participants experiencing Adverse Events (AEs) leading to permanent discontinuation of the study drug. [Time Frame: visit 1 to End of study visit].

- Frequency distribution (number & percent) of causes of treatment discontinuations. Chi² test will be used to determine *p*-value and significance between the 2 groups.
- Frequency distribution (number & percent) of occurrence of AEs necessitating a change or discontinuation of treatment. Chi² test will be used to determine *p*-value and significance between the 2 groups.

- Frequency distribution (number & percent) of type and severity of AEs. Chi² test will be used to determine *p*-value and significance between the 2 groups.

10.7.7 Primary Efficacy analysis:

A. Complete resolution for Pelvi- abdominal infection based on pelvi-abdominal Ultrasound

- Frequency distribution (number & percent) of complete resolution for pelvi-abdominal infection. Chi² test will be used to determine *p*-value and significance between the 2 groups.

B. Complete healing of the post-operative wounds [Time Frame: Follow-up 1 V to End of study visit].

- Frequency distribution (number & percent) of complete healing of the post-operative wounds. Chi² test will be used to determine *p*-value and significance between the 2 groups.
- Frequency distribution (number & percent) of incomplete healing of the post-operative wounds. Chi² test will be used to determine *p*-value and significance between the 2 groups.
- Frequency distribution (number & percent) of no healing of the post-operative wounds. Chi² test will be used to determine *p*-value and significance between the 2 groups.

10.7.8 Secondary Safety analysis:

A. Presence of any signs/symptoms of post-operative wound infection such as redness, fever or wound discharge [Time Frame: visit 1 to End of study visit].

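### The stated 80% power for a 2% non-inferiority margin is unsupported: at the control regimen's own cited 74% rate, 156 per arm gives about 11% power (one-sided 5%) or 6% (one-sided 2.5%)

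*Protocol*

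**What the plan says.** Protocol 10.5.1 opens the calculation with "As the primary objective is to assess the safety of oral" Ciprodiazole tablets, but the evidence it then cites is on efficacy: "Overall clinical resolution rates were statistically superior for CIP+MET (74%) compared with PIP/TAZO (63"%). The listed parameters are a non-inferiority design, 156 patients per arm, 80% power, "Confidence level 95% (α error = 5"%) and "Non-Inferiority margin = 2"%. SAP 7.1 repeats all of this. Neither document gives the rate assumed in each arm, the expected difference, the endpoint the margin applies to, the sidedness of alpha, or an allowance for patients who cannot be evaluated.

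Protocol 10.1 defines the comparator: "group B (control group): patients are treated with the currently used Ciprofloxacin Tablets & Metronidazole tablets". Piperacillin/tazobactam is not given in this trial.

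Protocol 10.7.1 restricts the efficacy population: "Analysis of all efficacy variables will be performed only for patients who completed the study without protocol violation (as per protocol"). For the first primary efficacy endpoint, protocol 10.7.7 plans: "Frequency distribution (number & percent) of complete resolution for pelvi-abdominal infection. Chi² test will be used to determine" the p-value. SAP 8.7 says the same. No confidence interval is compared with the 2% margin. Protocol 10.7.2 and SAP 8.2 describe the statistical section as specifications for a final SAP still to be issued.

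**The concern.** A power figure is meaningful only for stated rates, margin and alpha. Here the rates are missing, and the two that are cited belong to different regimens, only one of which is used in the trial. Both trial arms contain ciprofloxacin and metronidazole, so the obvious starting value for the control is 74%, and nothing in the documents supports a large true advantage for the fixed combination.

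A 2-point margin on a resolution rate near 74% normally needs thousands of patients, so 156 per arm looks far too few. If so, readers would credit the trial with power it does not have. Because only chi-squared tests are planned for primary efficacy, a non-significant result could be presented as non-inferiority backed by 80% power, when the data could not exclude differences several times the margin.

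**Working it through.** **Inputs.** From protocol 10.5.1 and SAP 7.1: n = 156 per arm, margin m = 0.02 (read as percentage points), power 80%, alpha 5%, cited rates 0.74 and 0.63. Sidedness is not stated, so one-sided 5% (z = 1.645) and one-sided 2.5% (z = 1.960) are both shown; z for 80% power is 0.842.

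**Formulas** (unpooled normal approximation; pc = control rate, pe = experimental rate):

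- n per arm = [pc(1−pc) + pe(1−pe)] × (z_α + z_β)² / (pe − pc + m)²
- power = Φ( (pe − pc + m) / √{[pc(1−pc) + pe(1−pe)]/n} − z_α )

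**Step 1: reproduce 156.** With pc = 0.63, pe = 0.74 and one-sided 5%: (0.2331 + 0.1924) × (1.645 + 0.842)² / 0.13² = 0.4255 × 6.183 / 0.0169 = 155.66, so 156 per arm. Other uses of the cited rates do not give 156:

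| pc / pe | one-sided 5% | one-sided 2.5% |
|---|---|---|
| 63% / 74% | **156** | 198 |
| 74% / 74% | 5,948 | 7,551 |
| 63% / 63% | 7,206 | 9,148 |

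A superiority comparison of 74% with 63% needs 220 (one-sided 5%) or 279 (two-sided 5%) per arm, so that is not the source either.

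**Step 2: power at the control regimen's cited rate.** With 74% in both arms, SE = √(2 × 0.74 × 0.26 / 156) = 0.0497 and 0.02 / 0.0497 = 0.403.

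- One-sided 5%: Φ(0.403 − 1.645) = 0.107.
- One-sided 2.5%: Φ(0.403 − 1.960) = 0.060.

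Exact binomial enumeration of the same rule gives 10.8% and 6.1%; a restricted-variance (Farrington-Manning) score test gives 10.8% and 5.9%.

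**Step 3: does the conclusion depend on 74%?** Power at 156 per arm for other common rates (assumed):

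| Rate in both arms | one-sided 5% | one-sided 2.5% |
|---|---|---|
| 63% | 10% | 6% |
| 90% | 15% | 9% |
| 95% | 20% | 13% |
| 98% | 35% | 24% |
| 99% | 55% | 43% |

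On this approximation, 80% is reached only at a common rate of about 99.5% (one-sided 5%) or 99.6% (one-sided 2.5%). With control at 74%, it needs a true advantage of 9.4 or 10.7 points. Even the fitted 63%/74% pair gives only 70% at one-sided 2.5%.

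**Step 4: what 156 per arm can support.** At 74% in both arms, the margin detectable with 80% power is 0.0497 × (z_α + z_β) = 12.3 points (one-sided 5%) or 13.9 points (one-sided 2.5%). The 95% CI half-width for the difference is 1.96 × 0.0497 = 9.7 points, nearly five times the margin.

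**The case against.** **The margin may concern safety.** Protocol 10.5.1 names safety as the objective. By symmetry, the same formula also returns about 156 per arm (one-sided 5%) for a common event rate near 0.507%, so 63%/74% is not the only possible origin. That is fair, and the back-fit should be treated as inference. But no document gives an event rate, and at an assumed 1%, 5% or 10% the approximate power (one-sided 5%) would be 55%, 20% or 15%.

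**Figures near 0% or 100% depend on the test.** This also stands. With no failures in either arm the unpooled standard error is zero and the rule passes automatically. The restricted-variance score test, enumerated exactly, gives 52.5% power at a common rate of 99.5% (one-sided 5%) and 25.7% at 99.6% (one-sided 2.5%); for 1% events it gives about 38% at one-sided 5%. The correction lowers power further and does not rescue the 80%.

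**Equal rates of 74% are an assumption.** The 74% comes from complicated infections treated intravenously and then orally. This trial's case mix is broader, wound healing has no cited rate, and the metronidazole schedules stated for the two arms differ (protocol 8.4.1 and 8.4.3). This limits the precision of 10.7% and 6.0%, but the range in Step 3 shows that it does not change the conclusion.

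**156 is not an arithmetic slip.** Agreed: it follows from one assignment of the cited rates. The defect lies in the unstated and unsupported inputs. A later final SAP could correct this, but the supplied SAP repeats the same statement.

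**Conclusion.** The concern holds and must be fixed. With 156 evaluable patients per arm, a 2-point margin and 74% in both arms, power is about 11% (one-sided 5%) or 6% (one-sided 2.5%), against the stated 80%. This rests on equal true rates, a margin in percentage points and no loss of patients.

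These are best-case numbers. Efficacy is analysed per protocol only, and because the trial enrols patients "who had pelvi-abdominal infection and/or started IV antibiotics for 48 hours", the infection and wound-healing endpoints may each apply to only part of the sample, although SAP Tables 9 and 10 print N=156 for both. The claim that the 63%/74% pair produced the 156 is inferred; the finding that 80% power is unsupported does not depend on it.

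**What to change.** Keep N = 312.

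- **Protocol 10.5.1 and SAP 7.1, assumptions:** name the endpoint the 2% margin applies to, the rate assumed in each arm with its source, the expected difference and the sidedness of alpha. If 156 came from a safety-event rate, give that rate.
- **Same sections, power:** withdraw the 80% claim for the 2% margin. State the recomputed power (about 11% at one-sided 5%, 6% at one-sided 2.5%, for 74% in both arms). State also that 156 evaluable per arm gives 80% power only for a margin of about 12.3 or 13.9 points respectively, with a 95% CI half-width of about 9.7 points. Label these as best case, for the reasons given above.
- **Protocol 10.7.7 and SAP 8.7:** add the risk difference with its 95% CI for each primary efficacy endpoint, and state that a non-significant chi-squared test will not be read as non-inferiority. A two-sided 95% CI corresponds to one-sided 2.5%. If the margin was meant for safety, add the same interval in protocol 10.7.6 and SAP 8.6.
- **Margin:** do not adopt a wider one unless it is justified clinically and independently of outcome data by arm.

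The cost is wording in two sections of each document and one interval per primary efficacy endpoint (more only if the margin concerns safety), with no extra patients. The stated power becomes much less favourable, and efficacy is reported mainly as an estimate with its interval.
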